#### 9.6 SUBJECT ACCOUNTABILITY

Once subject is screened and enrolled into the study the following study logs will be documented:

ficmi	– Study Protocol –	Protocol No.: FM-01 Version 5.1 Page 29 of 55
Safety and Usability Evaluation of the Fidmi Low-Profile Enteral Feeding Device		CONFIDENTIAL

Enrollment Log - Indicates all eligible subjects who signed the informed consent and were enrolled to the study. This log includes for each subject his/her subject identification number and the dates of signing the informed consent and of enrollment.

Subject Consenting Log – documents all subjects enrolled and details their ICF consenting details: date, ICF version, consenting investigator, re-consenting if required etc.

Patient Identification Log - Correlates the name and details of every subject with the relevant subject identification number. This log should be kept only at the investigational site.

Subject Visit log – list all planned visits (1-7) for each enrolled subject. This log can be filled further on the study conduct.

**10 TRIAL PROCEDURES** For study Schedule of Assessment, refer to

ficmedical	– Study Protocol –	Protocol No.: FM-01 Version 5.1 Page 30 of 55
Safety and Usability Evaluation of the Fidmi Low-Profile Enteral Feeding Device		CONFIDENTIAL

Table 3 - Visit procedure chart. No procedure or evaluation will be done prior to obtaining study consent.

After informed consent is obtained, a case record form (CRF) including all listed below will be recorded. Eligible patients will be enrolled into the study and be treated according to standard treatment protocols with PEG device insertion procedure with protocol local anesthetic.

#### **10.1 STUDY SPECIFIC PROCEDURES**

#### **10.1.1 PATIENT ENROLLMENT TO DISCHARGE**

#### Visit 1: Screening and Enrollment, as part of PEG pre-operative visit (can be performed up until 2 weeks before insertion procedure - visit 2)

Following signing of informed consent, patients scheduled and amenable for PEG insertion/replacement, will be screened for study enrollment by assessment of inclusion and exclusion criteria. The following assessments will be performed:

- Demographics (gender, age, race, ethnicity).
- Medical history (principal diagnosis requiring enteral nutrition, or hospitalization in the last 12 months).
- Vital signs
- Current medications.
- Physical examination.

Eligible patients will be enrolled into the study and be treated according to standard treatment protocols with PEG insertion/replacement.

The procedure for the PEG insertion/removal (Visit 2, see below) may be performed at the day of enrollment

#### Visit 2: Insertion/replacement of Fidmi device in the Endoscopy suite

If the procedure is taken on a different day than the inclusion day then the following assessments will be completed prior the procedure conducted:

a) Eligibility criteria

ficmedical	– Study Protocol –	Protocol No.: FM-01 Version 5.1 Page 31 of 55
Safety and Usability Evaluation of the Fidmi Low-Profile Enteral Feeding Device		CONFIDENTIAL

- b) Physical examination
- c) Vital signs

All patients will be operated by study delegated Gastroenterologist by the same method (see Investigator Brochure). Antibiotics will be administrated to patients on trial according to the investigator discretion.

The insertion procedure is performed by the investigator physician in a dimmed lighted room while the device is placed on a bedside tray under a protocol of local anesthetic.

Fidmi device method of insertion is detailed and illustrated in the Investigator Brochure.

An anonymous endoscopy recording of the procedure will be obtained for each patient.

Patients' charts will be reviewed and the following assessments will be completed following the procedure:

- d) Illuminated clear photos of the insertion/replacement site taken:
  - Frontal to the insertion site/ external bumper
  - Perpendicular (from the profile) to the insertion site/ external bumper
  - In close perspective if outstanding issues (medical or technical) are observed
- e) An anonymous endoscopy recording of the procedure

#### f) PEG Physician usability Form

#### **Study PEG insertion Form:**

insertion needed number of needle Re-puncture (sheath kink, loss of visualization), PEG insertion characteristics and duration, PEG placement location, Stoma Insertion/Removal site, Residual Tube above skin evaluation, heart rate at the end of the operation, time to resume typical enteric diet, amount and type of analgesia consumed, postoperative bleeding, use of antibleeding agents (such as tranexemic acid (hexakapron)).

ficmedical	– Study Protocol –	Protocol No.: FM-01 Version 5.1 Page 32 of 55
Safety and Usability Evaluation of the Fidmi Low-Profile Enteral Feeding Device		CONFIDENTIAL

Endoscopist feedback Form: Endoscopist 10-point Visual Analogue Scale for placement/removal procedure difficulty.

g) Study Patient Discharge form.

A study qualified personnel will instruct the patient before discharge with specific home instructions for use (IFU), maintenance, and instructions on how to periodically replace the Fidmi Disposable Feeding Tube when needed (see appendix in the IB). Together with the IFU leaflet the patient would be provided with his home Fidmi Disposable Feeding Tube pack. Instructions about the patient diet and medication should be given separately to the study.

The patient will be asked for his most convenient day for the Visit 3 follow up (see below) – this day will be recorded by the study nurse at the **Patient Visits Log**.

#### 10.1.2 PATIENT FOLLOW UPS AND PEG REMOVAL

Patients will be monitored for follow-up after 2, 30, 60 and 90 and 120 days following their PEG insertion/replacement procedure and will be evaluated by the study nurse for their medical conditions. PEG device removal will be conducted 3 months following its placement.

## Visit 3: Follow up 2 days (+/- 1 day) following procedure (sub-investigator visit in patient facility)

In compliance with the Centric Patient Approach, study delegated sub-investigator will visit the patient facility at the specific day scheduled together. The patient will be asked to report his nutritional status (malnutrition defined as a body mass index [BMI] <19 kg/m^2) and any stomal complication (wound infection, peristomal leakage, hypergranulation, pressure ulcer, any skin lesion adjacent to external bumper) – all will be investigated by the study **sub-investigator** using **Visit 3 safety Follow Up Form**.

ficm edical	– Study Protocol –	Protocol No.: FM-01 Version 5.1 Page 33 of 55
Safety and Usability Evaluation of the Fidmi Low-Profile Enteral Feeding Device		CONFIDENTIAL

In addition patient will be asked regarding his postoperative morbidity, any other Adverse Events and Concomitant medications.

Illuminated clear photos of the insertion site will be taken:

- Frontal to the insertion site/ external bumper
- Perpendicular (from the profile) to the insertion site/ external bumper
- In close perspective if outstanding issues (medical or technical) are observed

The study **sub-investigator** will also investigate tube performance: accidental dislodgement, buried bumper, gastric outlet obstruction, tube leakage, Residual Tube above skin evaluation, number of scheduled tube replacement, method of feeding (bolus, continues gravity, mechanical pump etc.), Scale 1-10 – ease of connecting the extension tube, ease of feeding, any replacements of disposable tubes other than scheduled (and reason) using Visit 3 Tube Utilization Form.

The following assessments will be conducted:

- a) Physical examination
- b) Vital signs

The patient will be asked for his most convenient day for his 30 days follow-up (Visit 4 follow up, see below) – this day will be recorded by the study nurse at the Patient Visits Log.

Visit 4: Follow up after 1 month +/- 10 days (sub-investigator visit in patient facility) In compliance with the Centric Patient Approach, delegated study sub-investigator will visit the patient facility at the specific day scheduled together. The patient will be asked to report his nutritional status (malnutrition defined as a body mass index [BMI] <19 kg/m^2) and any stomal complication (wound infection, peristomal leakage, hypergranulation, pressure ulcer, any skin lesion adjacent to external bumper) – all will be investigated by the study **sub-investigator** using **Visit 4 safety Follow Up Form**.

fich medical	– Study Protocol –	Protocol No.: FM-01 Version 5.1 Page 34 of 55
Safety and Usability Evaluation of the Fidmi Low-Profile Enteral Feeding Device		CONFIDENTIAL

In addition patient will be asked regarding his postoperative morbidity, any other Adverse Events and Concomitant medications.

Illuminated clear photos of the insertion site will be taken:

- Frontal to the insertion site/ external bumper
- Perpendicular (from the profile) to the insertion site/ external bumper
- In close perspective if outstanding issues (medical or technical) are observed

The study **sub-investigator** will also investigate tube performance: accidental dislodgement, buried bumper, gastric outlet obstruction, tube leakage, Residual Tube above skin evaluation, number of scheduled tube replacement, method of feeding (bolus, continues gravity, mechanical pump etc.), Scale 1-10 – ease of connecting the extension tube, ease of feeding, any replacements of disposable tubes other than scheduled (and reason) using **Visit 4 Tube Utilization Form**.

The following assessments will be conducted:

- a) Physical examination
- b) Vital signs

The patient will be asked for his most convenient day for the PEG removal hospital visit (Visit 6 follow up, see below) – this day will be recorded by the study nurse at the **Patient Visits Log**.

#### Visit 5: Follow up after 2 months +/- 10 days (phone call follow up)

In compliance with the Centric Patient Approach, delegated study member will call the patient facility at the specific day scheduled together. The patient will be asked to report his nutritional status (malnutrition defined as a body mass index [BMI] <19 kg/m^2) and any stomal complication (wound infection, peristomal leakage, hypergranulation, pressure ulcer, any skin lesion adjacent to external bumper) – all will be investigated by the study nurse using **Visit 5 safety Follow Up Form**. In addition

ficmedical	– Study Protocol –	Protocol No.: FM-01 Version 5.1 Page 35 of 55
Safety and Usability Evaluation of the Fidmi Low-Profile Enteral Feeding Device		CONFIDENTIAL

patient will be asked regarding his postoperative morbidity, any other Adverse Events and Concomitant medications.

The study personnel will also investigate tube performance: accidental dislodgement, buried bumper, gastric outlet obstruction, tube leakage, Residual Tube above skin evaluation, number of scheduled tube replacement, method of feeding (bolus, continues gravity, mechanical pump etc.), Scale 1-10 – ease of connecting the extension tube, ease of feeding, any replacements of disposable tubes other than scheduled (and reason) using Visit 5 Tube Utilization Form.

The patient will also be reminded for already scheduled day for the PEG removal hospital visit (Visit 6 follow up, see Patient Visits Log).

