#### Secondary:

- 10. To evaluate usability by Physician filling a user questionnaire.
- 11. To evaluate usability by the patient or caregiver during long term use filling a user questionnaire.

ficmedical	– Study Protocol –	Protocol No.: FM-01 Version 5.1 Page 24 of 55
Safety and Usability Evaluation of the Fidmi Low-Profile Enteral Feeding Device		CONFIDENTIAL

12. To be able to validate correct (color) selection of 'Measuring Cannula' by residual tube measurement [design endpoint]

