#### 10.2 SCALES AND EVALUATIONS

### Physical examination

A standard physical examination will be conducted on participating patients in all study visits. These will be conducted by the investigator or by any other authorized member of the study team.

Physical examination will include weight measurements, lungs, cardiovascular system, abdomen, musculoskeletal system, skin, lymph nodes, and central nervous system and, where appropriate, other body systems per discretion of investigator (see CRF).

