#### Vital signs

Vital signs (temperature, blood pressure, pulse rate, respiratory rate, and blood oxygen saturation) will be collected at all study visits.

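### The Visit 5 telephone call puts a reported residual-tube value into a measured series, section 10.2 contradicts Table 3 on examinations, and BMI <19 status is not tied to the weights taken

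*Protocol*

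**What the plan says.** **Visit 5.** Section 10.1.2 defines it as "Follow up after 2 months +/- 10 days (phone call follow up"). The caller must nevertheless cover accidental dislodgement and then "buried bumper, gastric outlet obstruction, tube leakage, Residual Tube above skin evaluation, number of scheduled tube replacement". Visits 3, 4 and 6, which are in person, carry the same list.

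**What the residual tube feeds.** Section 8.3 item 13 lists its measurement and evaluation at follow-up as a usability measure. Section 8.2 item 12 is a secondary endpoint: "To be able to validate correct (color) selection of 'Measuring Cannula' by residual tube measurement [design endpoint"]. Residual tube is also recorded at the end of placement (section 8.3 item 9, and the insertion form in section 10.1.1).

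**Nutritional status.** At Visits 3 to 7 the wording is in substance the same; at Visit 3 it reads "The patient will be asked to report his nutritional status (malnutrition defined as a body mass index [BMI] <19 kg/m"²). At Visit 5 the answers go to the nurse: "all will be investigated by the study nurse using" the visit's safety form.

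**Examinations.** Section 10.2 states "A standard physical examination will be conducted on participating patients in all study visits", names weight as part of that examination, and says vital signs "will be collected at all study visits". Table 3 schedules both at Visits 1, 2, 3, 4 and 6 only.

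**The concern.** A call cannot yield a measured residual tube, an inspected insertion site, a weight or vital signs. Table 3 has no site photographs at Visit 5 either, so no record exists from which a value could be checked later. Some patients are demented (section 9.3.2 provides for consent by a guardian), and Table 3 labels the tube form as one for the patient or caregiver. The month-2 answers may therefore be second-hand, and nothing in the protocol tells the person tabulating them to keep them apart from values seen by study staff.

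The conflict between section 10.2 and Table 3 has a practical consequence. Read literally, section 10.2 makes every completed Visit 5 a deviation, and section 13.4.1 requires all deviations to be logged and reported to the IRB.

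For nutrition, patients enter because dysphagia impairs, or is expected to impair, their nutritional status. A fixed cut-off put to the patient from day 2, with no entry status beside it, cannot distinguish a patient who arrived below 19 from one who fell below it while fed through the device.

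**Working it through.** The protocol gives no figure to reproduce: the analysis is descriptive and section 8.4 says no formal sample size calculation was done. The check sets sections 10.1.1, 10.1.2 and 10.2 beside Table 3, visit by visit.

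| Visit | Contact | Residual-tube item | Nutritional status asked | Exam with weight (Table 3) |
|---|---|---|---|---|
| 1 | pre-operative visit | no | no | yes |
| 2 | endoscopy suite | yes, insertion form | no | yes (section 10.1.1: before the procedure if on a different day from Visit 1) |
| 3 | sub-investigator on site | yes | yes | yes |
| 4 | sub-investigator on site | yes | yes | yes |
| 5 | telephone | yes | yes | no |
| 6 | hospital | yes | yes | yes |
| 7 | home X-ray plus call, or clinic | no, device already removed | yes | no |

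**Residual tube**
- Follow-up time points: Visits 3, 4, 5 and 6 = 4. By telephone: 1. Share 1/4 = 25%.
- Including placement (Visit 2): 1/5 = 20%.
- With the planned 15 patients, full attendance and no replacements: 15 × 5 = 75 values, of which 15 × 1 = 15 are telephone reports.

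**BMI <19 status**
- Follow-up time points: Visits 3 to 7 = 5.
- By telephone: Visit 5 always, and Visit 7 if the home X-ray is chosen, so 1/5 to 2/5 = 20% to 40%.
- Without a scheduled weight under Table 3: Visits 5 and 7 = 2/5 = 40%, whichever form Visit 7 takes. The clinic alternative at Visit 7 lists neither examination nor vital signs.

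**Section 10.2 against Table 3**
- Visits in the study: 7. Visits with examination and vital signs in Table 3: 5. Unmatched: 7 − 5 = 2 (Visits 5 and 7). At Visit 5 the text of section 10.1.2 also rules them out, because contact is by telephone.

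**What the cut-off can show**
- BMI is weight divided by height squared. Weight is named in section 10.2. Height is named neither there nor in the Visit 1 list, although the BMI >40 exclusion (section 9.2.2) cannot be applied without it.
- Illustration: a patient entering at BMI 18 meets <19 at every visit from day 2. A patient going from 30 to 20 loses (30 − 20)/30 = 33% of body weight and never meets it. At an assumed height of 1.70 m, 1.70² = 2.89, so weight goes from 30 × 2.89 = 86.7 kg to 20 × 2.89 = 57.8 kg, a loss of 28.9 kg. The case is deliberately extreme and shows only what the flag can and cannot register.

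**The case against.** The strongest reply is that little depends on the affected values. This is a descriptive feasibility study in 15 patients, BMI status appears in no endpoint list, and asking about complications by telephone is ordinary safety follow-up. The Visit 5 text asks for an evaluation, with no length or unit, and the form's label already discloses patient or caregiver input. Most of this stands and limits the size of the point. It does not remove the mixing of reported and measured values, or the contradiction over examinations.

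A reader might also infer four stronger things that the protocol does not support:

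- *That several telephone contacts spoil the residual-tube series.* Only Visit 5 does. The device is out before Visit 7, which has no such item.
- *That the cannula-validation endpoint is compromised.* The cannula is chosen at placement, and residual tube is recorded at the end of that procedure. No text says Visit 5 values enter the endpoint; the weakness is that none says they stay out.
- *That BMI <19 is purely patient-reported.* Study staff are to investigate the reported status, and at Visits 3, 4 and 6 the patient is also weighed. The protocol does not say that weight is disregarded; it is silent on whether it is used.
- *That no baseline exists.* Weight is part of the Visit 1 examination, the BMI >40 exclusion implies a screening BMI, and section 10.2 refers examination detail to the CRF, which is not at hand. Height may be collected there.

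How change from baseline is tabulated may properly be left to a statistical analysis plan. How a value is obtained, and whether it is marked as seen or reported, is settled at data collection and cannot be repaired afterwards.

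**Conclusion.** The point holds with limited effect. Three things are established from the text:

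1. One of four follow-up residual-tube time points is a report placed in a series described as measurement.
2. Section 10.2 contradicts Table 3 at two of seven visits, and at Visit 5 it cannot be carried out.
3. BMI <19 status is asked of the patient at five visits, two of them without a scheduled weight, with no stated link to the weights taken at Visits 1, 2, 3, 4 and 6 and no separation of entry status from new cases.

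The consequence is confined to descriptive safety and usability data. Residual tube is still assessed in person at Visits 2, 3, 4 and 6, and a large weight loss would show in the recorded weights whatever the flag said. The counts assume the visit schedule in Table 3, and the count of 75 assumes 15 patients with full attendance. Correction is worthwhile because it costs almost nothing and cannot be made once the data are in.

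**What to change.** - Reconcile section 10.2 with Table 3 and the Visit 5 and Visit 7 text, so that the visits requiring examination and vital signs are the same throughout.
- Keep the Visit 5 tube and buried-bumper questions, but mark the answers on the form as reported, not measured. Summarise them separately from the in-person values and state that they do not enter section 8.2 item 12. Deleting the buried-bumper question would be a mistake: section 6.1 lists it as a major complication, and Visit 5 is the only scheduled contact between months 1 and 3.
- Record at Visit 1 the height already needed for the BMI >40 exclusion, and calculate BMI from measured weight at each visit with a physical examination.
- Show change in BMI from baseline, with BMI <19 at entry separate from new BMI <19. Any status obtained without a weight should be labelled as reported.

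Cost: one height entry, small form edits, one paragraph in section 10.2 and one additional table. The downside is that there is no measured residual tube or BMI at month 2 and no measured BMI at month 4. The present schedule does not provide those measurements either; the change makes the gap visible.

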#### 3. PROTOCOL SYNOPSIS

Protocol Number	FM-01
Protocol Title	Safety and Usability Evaluation of the Fidmi Low-Profile Enteral Feeding Device
Participating Countries	IL
Study Type	Interventional
Study Design	The Fidmi trial is an early First In Human feasibility Open Label single center study consists of Single Group Assignment, to evaluate the safety and preliminary efficacy of Fidmi Low-Profile Enteral Feeding Device as a treatment for adult patients with a need for enteral feeding (Percutaneous Endoscopic Gastrostomy placement).
Investigational Study Device	Fidmi Feeding Device, by Fidmi Medical Ltd.

ficmedical,	– Study Protocol –	Protocol No.: FM-01 Version 5.1 Page 6 of 55
	6 1 - 1 1 1 1 1	

Safety and Usability Evaluation of the Fidmi Low-Profile Enteral Feeding Device

CONFIDENTIAL

Study Purpose	To evaluate the safety and effectiveness of the Fidmi PEG device: insertion, long term utilization, dismantling and removal		
Study Population	15 adult patients, male or female suffering from dysphagia, who are scheduled for PEG (Newly PEG insertion (minimum 10 patients) and PEG replacement involving endoscopy procedure)		
Study Procedures	15 Consecutive adult patients with need for enteral feeding Scheduled for PEG with protocol sedation. The patients will attend the following: Visit 1: Screening and Enrollment Visit 2: Insertion or replacement in the Endoscopy suite, Visit 3: Follow up after 2 days (sub-investigator visit in patient facility) Visit 4: Follow up after 1 month (sub-investigator visit in patient facility) Visit 5: Follow up after 2 month (phone call) Visit 6: Follow up after 3 months and Fidmi device removal Visit 7: Follow up after 4 months, X-ray and termination		
	
 
Safety Endpoints:
 
Number of Participants With Treatment-Related Adverse Events as Assessed by CTCAE v4.0 through study completion.
 
Number of participants requiring unscheduled hospital readmission related to Fidmi Feeding device through study completion.
 
Performance Endpoints:
 
		
Study Endpoints	
 
Primary:
 
3. Number of accidental dislodgements during study follow up until device removal at 3 months.
 
		
	
 
Number of unscheduled internal tube replacements (only clogged tubes) until device removal at 3 months.
 
		
	
 
Patient Pain on the Visual Analog Scale during device removal at 3 months.
 
		

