#### Visit 6: Follow up after 3 months +/- 10 and Fidmi device removal/replacement by balloon gastrostomy.

Prior to the procedure the patient will be asked to report his nutritional status (malnutrition defined as a body mass index [BMI] <19 kg/m^2) and any stomal complication (wound infection, peristomal leakage, hypergranulation, pressure ulcer, any skin lesion adjacent to external bumper) – all will be investigated by the study nurse using Visit 6 safety Follow Up Form. In addition patient will be asked regarding his postoperative morbidity, any other Adverse Events, Concomitant medications.

Illuminated clear photos of the insertion site will be taken:

- Frontal to the insertion site/ external bumper
- Perpendicular (from the profile) to the insertion site/ external bumper
- In close perspective if outstanding issues (medical or technical) are observed

Study nurse will also investigate tube performance: accidental dislodgement, buried bumper, gastric outlet obstruction, tube leakage, Residual Tube above skin evaluation, number of scheduled tube replacement, method of feeding (bolus, continues gravity, mechanical pump etc.), Scale 1-10 – ease of connecting the extension tube, ease of feeding, any replacements of disposable tubes other than scheduled (and reason) using Visit 6 Tube Utilization Form

ficmedical	– Study Protocol –	Protocol No.: FM-01 Version 5.1 Page 36 of 55
Safety and Usability Evaluation of the Fidmi Low-Profile Enteral Feeding Device		CONFIDENTIAL

The following assessments will be conducted prior to device removal/ replacement by balloon gastrostomy:

- a) Physical examination
- b) Vital signs

\*An endoscopic examination is not required but may be performed on a need base, and following the investigator discretion.

In case a Gastrostom replacement is required, the study investigator will advise the patient from various types of technologically equivalent or similar devices including 'low profile' types. The replacement procedure will be performed routinely as specified in the Instruction for Use.

The following assessments will be conducted following the device removal/ replacement by balloon gastrostomy:

c) PEG Physician usability Form

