#### Table 3 - Visit procedure chart

	Enroll and d place	evice		Follow	/ Up Per	iod	
Procedure	Screening & Enrollment	Fidmi device insertion	Sub-I visit in patient facility	Sub-I visit in patient facility	Follow up call with the patient	Fidmi device removal	X-ray and termination visit
Visits	V1	V2	V3	V4	V5	V6	V7
Time Schedule (Days)	-7	0	2	30	60	90	120
Time Window (+/- Days)	7		1	10	10	10	14
Informed consent	Х						
Demographics+ Med. history	Х						
Concomitant medications	Х	х					
Physical exam	Х	x	х	х		х	
Vital signs	Х	x	х	х		х	
Adverse event evaluation		x					
Endoscopy recording		x					
Photos of the insertion site		x	х	х		х	
PEG usability Form (physician)		х				х	
Patient Discharge form		х				х	
Safety Follow Up Form			Х	Х	Х	х	x
Tube Utilization Form (patient/care giver)			х	х	х	x	
Patient feedback Form						х	
Patient Bumper flanges							
expulsion Form							х
X-ray imaging (home/clinic)							х
Post PEG removal imaging Form							х
Termination Visit							х
Subject Visit log		Х	Х	Х	Х	х	
Un-scheduled visit Form (if needed)							

F medical	– Study Protocol –	Protocol No.: FM-01 Version 5.1 Page 40 of 55
Safety and Usability Evaluation	of the Fidmi Low-Profile	
Enteral Feeding Device		CONFIDENTIAL

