# 13.5.5 DEVICE ACCOUNTABILITY

Accountability records must be maintained at the site at all times. The identification number of the subject, the supply/shipment date, lot number, expiry date, usage and disposal date of the Fidmi device and the date and quantity of devices returned will be recorded and maintained by the PI.

At study conclusion, all devices (used and unused) must be returned to the sponsor or sponsor's designee for destruction and documented evidence of destruction should be available. Ancillary supplies may not have to be returned.

Upon Fidmi/Fidmi designee visit at the site, accountability of the returned devices should be performed and recorded.

Safety and Usability Evaluation of the Fidmi Low-Profile **Enteral Feeding Device** 

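### The primary count of clogged-tube replacements rests mainly on patient or caregiver report at contacts up to 50 days apart, with no tube-change log prescribed

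*Protocol*

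**What the plan says.** The Synopsis (Section 3, Study Endpoints, item 4) sets as a primary performance endpoint the "Number of unscheduled internal tube replacements (only clogged tubes) until device removal at 3 months". Section 8.2 carries the same endpoint, worded as a rate.

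Section 5.2 says that the patient or caregiver changes the disposable tube. At discharge from Visit 2 (Section 10.1.1) the patient receives a leaflet, a home pack of tubes and "instructions on how to periodically replace the Fidmi Disposable Feeding Tube when needed". Section 9.3.2 provides for patients with dementia, with consent by a guardian.

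Under Section 10.1.2, staff ask at Visit 5, by telephone, about "any replacements of disposable tubes other than scheduled (and reason) using Visit 5 Tube Utilization Form". Visits 3, 4 and 6 carry the same item, together with the number of scheduled changes. Table 3 names the informant in the title of the form: "Tube Utilization Form (patient/care giver".

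Section 13.5.2 mentions diaries in a general description of source documents. The list of sources for this trial that follows names no tube log. Section 13.5.5 requires used and unused devices to be returned at study conclusion, and usage, disposal date and returned quantity to be recorded. It then adds: "Ancillary supplies may not have to be returned".

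**The concern.** Each endpoint event needs two facts: that the change was off schedule, and that clogging was the reason. Both arise at home, out of the study team's sight, and are asked for weeks later, once by telephone. The informant may be a caregiver answering for someone with dementia. An event that is forgotten leaves no trace in the form. A clog remembered as jamming or leakage leaves the clogged-only count, and Section 8.3 treats jamming and leakage as separate tube-performance items.

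Resistance to clogging is one of the main claims made for the device (Sections 5.1 to 5.3). With 15 patients and no control arm, a few lost or misassigned events can change how the reported count looks beside the 12.5-45% clogging incidence that Section 5.1 cites for existing tubes. An analysis plan cannot repair this, because it cannot recover changes that were never recorded.

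**Working it through.** The protocol states no recall interval and no expected count, so there is no figure of its own to reproduce. The gaps follow from the visit windows.

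**Inputs (Section 10.1.2 and Table 3)**
- Visit 3: day 2 ± 1, so days 1 to 3.
- "Visit 4: Follow up after 1 month +/- 10 days": days 20 to 40.
- "Visit 5: Follow up after 2 months +/- 10 days (phone call follow up": days 50 to 70.
- "Visit 6: Follow up after 3 months +/- 10 and Fidmi device removal/replacement by balloon gastrostomy": days 80 to 100.

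**Gap between contacts.** Longest = latest day of the later visit − earliest day of the earlier visit. Shortest = earliest day of the later visit − latest day of the earlier visit.

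| Gap | Nominal (days) | Shortest (days) | Longest (days) |
|---|---|---|---|
| Visit 3 to 4 | 30 − 2 = 28 | 20 − 3 = 17 | 40 − 1 = 39 |
| Visit 4 to 5 | 60 − 30 = 30 | 50 − 40 = 10 | 70 − 20 = 50 |
| Visit 5 to 6 | 90 − 60 = 30 | 80 − 70 = 10 | 100 − 50 = 50 |

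The two 50-day gaps exclude each other. A 50-day gap from Visit 4 to 5 puts Visit 5 on day 70, which leaves at most 100 − 70 = 30 days to Visit 6. If the Visit 5 call were missed, Visit 4 to Visit 6 could span 100 − 20 = 80 days.

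**Routine changes among which a clog-driven one must be told apart.** The protocol gives more than one interval, so both ends are shown:
- Nominal 30-day gap: 30/14 = 2.1 to 30/7 = 4.3, so 2 to 4 changes.
- Longest 50-day gap: 50/14 = 3.6 to 50/7 = 7.1, so 3 to 7 changes.
- 90 days in place, counting changes before removal: 89/14 = 6.4 to 89/7 = 12.7, so 6 to 12 changes.

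**What counts as scheduled.** Section 5.2 gives every 1-2 weeks in the device description and each 2 weeks in the parts list after Table 2. The Visit 2 discharge text speaks of periodic replacement when needed. Take a change on day 9. It lies inside the first interval, it is early under the second, and the third sets no schedule against which to judge it.

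**Whether returns can check the count.** The parts list after Table 2 names the disposable feeding tube as one of the device's three main parts, while Table 2 itself lists disposable tubes under Accessories. Section 13.5.5 therefore leaves open whether they are returned devices or exempt supplies. It also does not link returns to the Tube Utilization Form. A returned tube would show that a change took place, but not why.

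**Illustration only.** Let p be the chance that a patient has a clog and r the fraction of such patients recorded. The recorded number expected among 15 is 15·p·r, and the chance of recording none is (1 − p·r)^15. Using the cited 12.5% and 45% as p is an assumption, since those figures refer to the life of existing tubes. The values of r are also assumptions.
- p = 12.5%, r = 100%: 1.9 expected; chance of none 13%.
- p = 12.5%, r = 50%: 0.9 expected; chance of none 38%.
- p = 45%, r = 100%: 6.8 expected; chance of none 0.01%.
- p = 45%, r = 50%: 3.4 expected; chance of none 2%.

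**The case against.** The strongest reply is that the protocol has more safeguards than the form alone.

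- Tube clogging is an anticipated adverse event (Section 11.1), adverse events are collected throughout (Section 11.3), and patients have a 24-hour call line (Section 11.2). This is a real second route. However, follow-up questions about adverse events are asked at the same contacts, and a clog solved by changing a tube at home need not prompt a call.
- At Visits 3 and 4 a sub-investigator attends in person and could see the remaining packs. Section 5.4.1 supplies five disposable-tube packs per patient, so changes reported could be compared with packs supplied. No such comparison is prescribed, and the number of tubes per pack is not stated.
- The form already takes unscheduled changes for any reason, and Section 12 tabulates all data in the case report form. This stands: a misassigned reason leaves the clogged-only count but not the dataset.
- The form, the case report form and the home instructions are not in the protocol and may contain a change record. That cannot be excluded. The point is that the protocol prescribes none.
- The study is a small, descriptive feasibility trial with no threshold on this count. This limits the consequence.

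A reader might go further and infer that tube returns are not checked at all, or that events are under-counted in the device's favour. The document supports neither. Section 13.5.5 does require devices to be returned and recorded; only the status of the disposable tubes is unclear. Forgetting can only remove events, so under-counting is the likelier direction. But a routine change may be remembered as an unscheduled clog, or jamming as clogging, so the net direction is not established.

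**Conclusion.** The point holds as a weakness in data collection. A primary endpoint depends mainly on retrospective patient or caregiver report of both number and cause, over gaps of nominally 28 to 30 days and at most 50. There is no prescribed contemporaneous record and no stated reconciliation with tubes used. The gaps are firm, since they follow directly from the visit windows. The size of the error is unknown: the document gives no recall rate, and the illustration rests on assumed values. A lower count is likely but not certain, given the inconsistent change interval. Because no decision rule hangs on the count, this is a worthwhile, inexpensive improvement and does not invalidate the study.

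**What to change.** 1. Add a one-page log to the home pack given at Visit 2, with date, scheduled or not, and reason for each change. Read it at Visits 3 to 6 when the Tube Utilization Form is completed, and name it in the trial-specific source list in Section 13.5.2.
2. State in Section 13.5.5 that disposable tubes are accountable items, used and unused, counted at Visit 6 and reconciled with the log and the forms.
3. Reconcile the two statements in Section 5.2 and the Visit 2 discharge text so that unscheduled has one meaning. Without this, the log's scheduled-or-not column inherits the ambiguity. Which interval applies is for the sponsor and investigators to settle.
4. Report the all-reason unscheduled replacements, which are already collected, next to the clogged-only count, so that readers can see how far the result depends on the reason given.

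The cost is one printed sheet, one line of writing per change for the patient or caregiver, and a tube count at an existing visit. No visit is added.
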